7.3.7 SCHEDULE OF EVENTS TABLE

Schedule of Events Timepoint/Visit	Screen	Baseline	ARM 1 - PreDischarge from SSU	ARM 2 - PreDischarge from Hospital Floor	30-Day & 90 Day Follow up
Informed Consent	X				
Medical History		X			
Physical Exam		X	X	X	
Clinical lab tests*		X	X~	X~	
ECG*		X			
CXR*		X			
KCCQ (QoL) & SF-12			X	X	X
Oberst Caregiving Burden Scale and Bakas Caregiving Outcomes Scale			X	X	X ¹
HF Guideline Assessment			X	X	
Collect concomitant meds		X	X	X	
mRUQ-HF (resource utilization)					X ²
Cost Effectiveness Measures (i.e. DRG)					X
Guideline adherence assessment		X	X	X	X ¹
SCPC Discharge Criteria Adherence			X	X	
Assessment of AE/SAE's through 5 days			X	X	
Vital Status, ED visits, Hospital days, Re-admission status			X	X	X
Subject Payment			X	X	X ²

*per standard of care. Typical labs include: Na, K, renal function, HgB, troponin, Natriuretic Peptide levels. ~only if performed per usual care

SOC = standard of care, ED = Emergency Department, QoL = quality of life, HF = heart failure, mRUQ = modified resource utilization questionnaire, EMR = electronic medical record, DRG = diagnosis related group

¹Only through 30 days

²Sites may choose to make a single payment or to divide into 2 payments.

³only at 90 days

NOTE: If patients are hospitalized from the SSU, ONLY the following assessments should be collected. Otherwise, the pre-discharge assessments will apply.

- Physical exam
- Clinical lab tests
- Con meds
- SCPC discharge criteria. This would be conducted twice. Once in SCPS prior to hospitalization and again at discharge.

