10.1.1 ENDPOINTS AND RATIONALE

To ensure patient-centered endpoints, we twice met with patients and caregivers through two community engagement studios.⁵⁴ Patients prefer to be healthy and have a good QoL. If a safe alternative is available, patients prefer not to be hospitalized.

The **primary outcome** is **days alive and out of hospital (DAOOH) at 30 days post-randomization**. Unlike time-to-event analyses that ignores repeat events and gives equal weight to components of a composite endpoint,⁵⁵ DAOOH accounts for both frequency and duration of hospitalization and also weights mortality most heavily.^{55,56} This endpoint has also been suggested as a quality metric rather than re-hospitalization alone.⁵⁷

The **two secondary outcomes** are 1) **QoL using the KCCQ**. Patients desire not only to live longer, but to live better; or at minimum, not be worse after an acute health care related event.⁵⁸ Patients with advanced HF would trade survival time (or days alive) for a better QoL.⁵⁸ Our pilot work supports the feasibility of assessing QoL in the acute setting and suggests changes in scores are related to hospital re-visits.⁵⁹ We hypothesize that fewer days in the hospital in our SSU arm will also lead to a greater QoL. Interviews of hospitalized AHF patients suggest **they would prefer a shorter hospital stay or avoid an admission altogether**, assuming safety and outcomes are similar or better than hospitalization. Thus, assessing QoL is a key aim.

The KCCQ is a patient-reported, validated survey instrument designed to measure QoL in chronic HF patients.⁶⁰ Lower scores equal lower patient-reported QoL. **KCCQ scores predict adverse outcomes – namely hospitalization and mortality.** Importantly, the KCCQ demonstrates responsiveness to clinical change.⁶⁰⁻⁶²

A change of five points has been previously shown to be clinically significant, and will be assessed prior to discharge and day 30 post-randomization.⁶²

2) Cost effectiveness analysis, described in detail below.

NOTE: For patients randomized to SSU who worsen PRIOR to going to SSU, this will be counted the same as a hospitalization from the SSU.

ADDITIONAL ENDPOINTS

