10.2 STATISTICAL HYPOTHESES

Aim 1: To demonstrate the effectiveness of a SSU AHF management strategy vs. usual AHF care (i.e. inpatient admission), using a randomized, controlled, simple trial design.

- **Hypothesis 1a:** SSU treated patients will have one more DAOOH within 30 days post-randomization vs. usual care arm. Assuming a 10% attrition rate, we will randomize 534 patients 1:1, which will provide 80% power (alpha 0.05, two-sided) to demonstrate a one-day difference in the primary outcome at 30 days post-randomization.
- **Hypothesis 1b:** An AHF SSU strategy of care will lead to significant improvement in QoL scores at 30 days post-discharge compared with usual care. QoL will be assessed with the KCCQ.⁵⁹

Aim 2: To demonstrate if a SSU AHF strategy of care leads to equivalent or improved adherence to HF guidelines at time of discharge compared to usual care.

- **Hypothesis 2:** Adherence to HF guidelines at time of discharge in the SSU arm is equivalent or better than adherence in the usual care arm.

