10.4.3.1 ADDITIONAL ANALYSES

Exploratory Analyses: As observation is not an admission, payers cover out of pocket costs differently.

Guideline Adherence: Adherence to HF guidelines at time of discharge in the SSU arm is equivalent or better than adherence in the usual care arm.

Sample Size Calculation: We assume that the adherence percentage is 85% in the control arm.⁶⁴ With 240 subjects in each arm, we will have 80% power to detect an absolute improvement of 8% in the SSU arm, where the type I error rate is controlled at 0.05 (two-sided). Adherence to HF-Guidelines will be assessed based on the established Get-With-The-Guidelines HF (GWTG-HF) metrics for eligible patients. These measures have been previously well established.^{64,74}

HF Guideline Adherence Analysis: Fisher's exact test will be used to compare the percentage of adherence. Please see below regarding sensitivity analysis and missing data approaches.

CB Scale: Sample size (both arms combined)	% of data attrition	Effect size in CB scale
480	10%	0.25
360	33%	0.30
240	55%	0.37
120	78%	0.51

Caregiver Burden Analysis: This will be similar to the KCCQ analysis. See table for sample size considerations.

Sub-group analysis: The nature of the sub-group analysis is exploratory and will be used to generate hypotheses for future testing. We will study four pre-specified sub-groups: 1) older patients, defined as greater than 75 years old; 2) gender; 3) race and 4) insurance status (Medicaid, self-pay, Medicare, Commercial). The rationale for selecting these sub-groups is based either on known cardiovascular disparities or there is limited data regarding an SSU strategy in these specific subgroups.⁴⁶ The hypothesis: there will be no differences in outcomes, QoL, or guideline adherence between any of these groups. If the primary endpoint is achieved, we aim to demonstrate the AHF SSU strategy is broadly applicable across all subgroups. If there are differences, however, this may either demonstrate areas in need of further study, or initial subgroups to target. To test these hypotheses, we will compare the treatment benefit between sub-groups by formal two-sample testing procedures using normal approximation (e.g. Z test). A permutation test will also be performed as a sensitivity analysis. Given the limited sample size and the exploratory nature of the sub-group analysis, no multiple comparison adjustment will be made for these tests.

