10.5 SAMPLE SIZE

A one-day difference in the length of hospital stay is a 20% reduction in the mean length of stay(LOS) of five days during hospitalization (median LOS =4.3 days).⁵⁰ Pilot data support the clinical significance of a one-day reduction,⁴⁵ and discussions with patients and caregivers confirms this finding. *While we anticipate achieving greater than a one-day difference, we have powered our study conservatively.*

$$N (\text{total}) = 534; \quad N_1 = 267; \quad N_2 = 267$$

Based on published data,⁴⁶ we project that DAOOH has a mean of 25.6 with a standard deviation of 3.9 in the control arm. A reduction of the mean DAOOH by one-day is the minimal clinically meaningful difference as determined through our patient engagement outreach.⁵⁴ An interim analysis when half of the outcome data are available will be performed. (See DSMB, section E6). Accounting for this with the O'Brien-Fleming spending function, 240 subjects per arm are required to achieve 80% power in detecting the one-day difference in DAOOH, where the two-sided type I error rate is controlled at 0.05. Assuming 10% attrition due to drop-outs and lost to follow up, this study requires a total of 534 subjects. This power calculation also takes into account a conservative estimate of 40% of patients being admitted to the hospital from the SSU arm. *DAOOH automatically accounts for death.* The maximal number of days alive and out of the hospital through 30 days post randomization is 30 days. If a patient were to die on day 8 post-randomization, her DAOOH would be 8. This would be compared to a patient who stayed in the hospital 3 days after randomization, but never returned to the ED or hospital or died through 30 days. DAOOH of this patient would be 27. If the same patient returned to the hospital on day 12 for 2 days, and again on day 24 for 2 days, their total DAOOH would be 23.

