10.6 MEASURES TO MINIMIZE BIAS

10.6.1 ENROLLMENT/ RANDOMIZATION/ MASKING PROCEDURES

Patients will be randomized 1:1 to one of the two study arms, but stratified by site to ensure equal site representation. A central computer generated randomization scheme with random block sizes of two, four, and six will be created, stratified by site. The REDCap randomization module will be utilized to generate the randomization schema and patient allocation.

Due the nature of the intervention and the clinical setting, this is an unblinded trial.

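### As written, the Schedule of Events NOTE would leave SSU patients who are then hospitalized without the discharge adherence, KCCQ, SF-12 and caregiver assessments scheduled for every usual-care patient

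*Combined protocol and SAP*

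**What the plan says.** The table in 7.3.7 gives each arm one pre-discharge column: from the SSU for Arm 1 and from the hospital floor for Arm 2. Both columns mark KCCQ and SF-12, the two caregiver scales, the guideline rows, SCPC criteria, AE/SAE assessment, and vital status with hospital days. The NOTE then says: "If patients are hospitalized from the SSU, ONLY the following assessments should be collected. Otherwise, the pre-discharge assessments will apply". The list that follows has four items: physical exam, clinical labs, concomitant medications and SCPC discharge criteria. Timing is given for the SCPC criteria alone: "This would be conducted twice. Once in SCPS prior to hospitalization and again at discharge".

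The rest of the plan makes no exception for SSU patients who are admitted:

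- Hypothesis 2 (10.2) reads: "Adherence to HF guidelines at time of discharge in the SSU arm is equivalent or better than adherence in the usual care arm".
- Section 10.1.1 measures adherence at discharge in both arms, and the KCCQ and caregiver scales before discharge.
- The cost-effectiveness text in 10.4.3 has the SF-12 completed at the start and end of the episode, and puts the baseline score in every effectiveness model.
- The Full Analysis Set (10.3) takes all randomized patients as randomized.

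Admission after the SSU is part of the strategy under test (2.3.1, 6.1.2). Section 10.5 plans for "a conservative estimate of 40% of patients being admitted to the hospital from the SSU arm". Section 10.1.1 adds: "For patients randomized to SSU who worsen PRIOR to going to SSU, this will be counted the same as a hospitalization from the SSU".

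**The concern.** Followed literally, the NOTE creates missing data in one arm only, and a post-randomization outcome (failure of short-stay care) decides who is missing. Usual-care patients are assessed at discharge whatever their course.

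Two groups of analyses are exposed. The first is Aim 2, which is defined at discharge. The second is any analysis that uses the discharge KCCQ, SF-12 or caregiver value. The table schedules none of these instruments at baseline, so the pre-discharge visit is the first measurement. It is therefore the starting point for change scores and the only candidate in the table for the SF-12 baseline score in the cost-effectiveness models.

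The missing-data plan in 10.4.5 (multiple imputation under MAR, an MNAR sensitivity analysis if MNAR is a concern, and a report that ignores missing data) does not safely repair this. No admitted SSU patient would have an observed discharge value, so imputing for that group would extrapolate from patients with a different course.

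**Working it through.** **Inputs.** Control adherence 85%, an 8-point improvement, 240 per arm, two-sided 0.05 and Fisher's exact test (10.4.3.1). Admission rate 40%, 267 randomized per arm and 10% attrition (10.5). KCCQ-change SD 20.8 (10.4.3). A KCCQ change of 5 points counts as clinically significant (10.1.1). The 20% admission rate and all gaps below are assumptions; the documents give no such figures.

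**1. Reproduce the plan's figure.** Section 10.4.3.1 states: "With 240 subjects in each arm, we will have 80% power to detect an absolute improvement of 8% in the SSU arm". With p1 = 0.85, p2 = 0.93 and pooled proportion p̄:

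power = Φ{[0.08 − 1.96·√(p̄(1−p̄)(1/n1+1/n2))] / √(p1(1−p1)/n1 + p2(1−p2)/n2)}

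For 240 vs 240, p̄ = 0.890: (0.08 − 1.96 × 0.02856)/0.02833 = 0.848, so power is 80.2%. The stated figure reproduces. Exact Fisher power is 76.8%.

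**2. Patients without discharge values under the literal reading.**

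- At 40%: 0.40 × 267 ≈ 107 randomized, or 0.40 × 240 = 96 evaluable. That leaves 144 SSU vs 240 usual care.
- At 20%: 0.20 × 240 = 48 evaluable. That leaves 192 vs 240.

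**3. Aim 2 power for 85% vs 93%.**

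- 240 vs 144 (p̄ = 0.880): (0.08 − 1.96 × 0.03425)/0.03136 = 0.410, so power is 65.9% (Fisher 64.5%). The difference detectable with 80% power rises from 8 to about 9.2 points.
- 240 vs 192 (p̄ = 0.8856): (0.08 − 1.96 × 0.03082)/0.02950 = 0.664, so power is 74.7%.

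**4. KCCQ change.** Detectable difference = (1.96 + 0.842) × 20.8 × √(1/n1 + 1/n2).

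- 240 vs 240: 5.3, as in the plan's table.
- 240 vs 144: 6.1.

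**5. Selection bias.** Let f be the admission rate and g the mean in discharged SSU patients minus the mean in admitted SSU patients. The whole-arm mean equals the discharged mean minus f × g, so an analysis of discharged patients only is off by f × g. The sign of g is unknown. The table takes g as positive, f = 0.40 and no true difference between the randomized arms (85% in both).

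| Assumed adherence gap | Spurious difference | Chance of p < 0.05, 240 vs 144 (Fisher) |
|---|---|---|
| 5 points | 2 points | 7.5% (7%) |
| 10 points | 4 points | 19% (17%) |
| 20 points | 8 points | 66% (65%) |

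At f = 0.20 the same gaps give 1, 2 and 4 points. For KCCQ change at f = 0.40, assumed gaps of 5, 10 and 15 points give 2, 4 and 6 points, against the 5-point clinical threshold.

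**The case against.** The strongest reply is that the NOTE was never meant this way. It can be read as naming what is done at transfer to the ward, with the ordinary pre-discharge set to follow at final discharge. The literal reading would also drop the AE/SAE row and the vital-status and hospital-days row for admitted SSU patients. Section 8.4.1 requires AE reporting for 5 days after randomization, and the primary endpoint counts inpatient hours (10.4.2), so those omissions can hardly be intended. The mention of a repeat at discharge shows that an assessment at that point was foreseen. This stands as evidence of a drafting fault, but it does not remove the risk. No section states the transfer-only reading. Singling out SCPC as done twice suggests that the other items are done once, and the only Arm 1 discharge column is from the SSU. Sites could divide on it.

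Three further limits stand:

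- **Scope.** The 30-day KCCQ and SF-12, the 30-day caregiver scales and the 30-day adherence assessment carry no exception (7.3.3, 7.3.7). Hypothesis 1b is set at 30 days. Adherence and caregiver burden are exploratory endpoints, and 4.2.3 even places adherence at 30 days, although Aim 2 and the synopsis place it at discharge.
- **Recovery.** Concomitant medications are on the short list, discharge summaries are examined (8.4.1) and records are reviewed (10.4.5). Some adherence items could be rebuilt. The full composite is not assured, and questionnaires cannot be collected afterwards.
- **Size.** The 40% is a conservative planning value. The gaps are assumed.

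**Conclusion.** The point holds as a conflict between the NOTE and 10.1.1, 10.3 and the cost-effectiveness text in 10.4.3, with a serious consequence if sites follow the NOTE as written. On that condition, and at 40% admitted, 96 of 240 evaluable SSU patients lack discharge values, Aim 2 power falls from 80% to about 66%, and the SSU estimate is biased by 0.4 times an unknown gap. At an assumed 20%, 48 are lost and power is about 75%. The lost power is the smaller problem; the larger one is that Aim 2 would no longer be a randomized comparison. If every SSU patient is assessed at final discharge, the stated 240 vs 240 figures stand.

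A reader might infer more than the documents support. They do not show that the plan sets out to measure discharge outcomes only in SSU successes, because a second reading is open. They do not show that the quality-of-life results as a whole are compromised, because the 30-day values are collected in everyone and only change scores and baseline-adjusted models are exposed. Nor do they show that a favourable adherence result would be selection alone, since neither the size nor the direction of the gap is given. Patients who worsen before reaching the SSU may enlarge the affected group, but the plan does not say whether the NOTE applies to them.

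**What to change.** Three edits settle both readings:

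1. Reword the NOTE so that the four items are collected at SSU-to-inpatient transfer in addition to the full pre-discharge set at final discharge: KCCQ, SF-12, caregiver scales, guideline rows, AE/SAE, and vital status with hospital days. Say whether it also covers patients who worsen before reaching the SSU.
2. Retitle the Arm 1 column, or add one, so that it covers discharge from hospital after the SSU.
3. State in 10.2 and 10.4.3.1 that time of discharge means the final discharge of the index episode for every randomized patient.

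The cost is an amendment to a footnote, a column heading and two sentences, plus existing forms completed at final discharge for up to about 107 SSU patients. Usual-care patients already complete the same forms before leaving the hospital. If enrollment has begun, report how each site has applied the NOTE and how many discharge assessments are missing in admitted SSU patients.

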7.5 CONCOMITANT MEDICATIONS

All medications administered within 14 days prior to and during screening will be recorded in the case report form. Medications that are not specifically prohibited are permitted at the Investigator's discretion.

7.6 PROHIBITED MEDICATIONS, TREATMENTS, AND PROCEDURES

No medications, treatments, or procedures are prohibited unless specifically mentioned in the eligibility criteria. Patient safety and well-being are paramount: Any treatment deemed necessary may be utilized at the investigators discretion should there be any concern for the patients health.

8 ASSESSMENT OF SAFETY

In addition to standard safety monitoring by the sponsor, an independent DSMB will oversee patient safety in the trial. The DSMB will meet as specified in its charter.

8.1 SPECIFICATION OF SAFETY PARAMETERS

Mortality, re-hospitalization, and ED visits through 30 and 90 days will be assessed for safety as well as efficacy

8.1.1 DEFINITION OF ADVERSE EVENTS (AE)

The Investigator and study staff are responsible for detecting and recording AEs and SAEs during scheduled safety evaluations and whenever such information is brought to their attention. This section of the protocol provides definitions and detailed procedures to be followed. During each visit, the Investigator will question the patient about adverse events using an open question, taking care not to influence the patient's answers, e.g. "Have you had any unusual symptoms or medical problems since the last visit? If yes, please describe."

An AE is any unfavorable and unintended sign, symptom, or disease temporally associated with the use of an investigational (medicinal) product or other protocol-imposed intervention, regardless of attribution. It is expected that many HF patients will have events that are commonplace due to their HF and associated comorbidities. Our study plans to focus on AE that are outside of what is typically encountered during an AHF event and the subsequent 90 days.

This includes the following:

- AEs not previously observed in the subject that emerge during the protocol-specified AE reporting period (5 days for anything other than mortality, re-hospitalization, and ED visits)
- Complications that occur as a result of protocol-mandated interventions such as a medication adjustment
- Preexisting medical conditions (other than the condition being studied) judged by the investigator to have worsened in severity or frequency or changed in character during the protocol-specified AE reporting period that are outside of what would be expected for a patient with AHF or HF in the outpatient setting.

For example, a patient upgraded to ICU status from the observation or SSU. Hospitalization, by itself, does NOT count as it is expected to occur for a proportion of SSU patients.

- Abnormal laboratory values that fall into an abnormal range based upon the hospital's laboratory standards, the abnormality was not preexisting prior to enrollment, and the abnormality leads to a new treatment within the AE time frame, with the exception of repleting potassium.

8.1.2 DEFINITION OF SERIOUS ADVERSE EVENTS (SAE)

An AE will be classified as an SAE if:

- It results in death (i.e., the AE actually causes or leads to death).
- It is life threatening (i.e., the AE, in the view of the investigator, places the subject at immediate risk of death. It does not include an AE that, had it occurred in a more severe form, might have caused death).
- It requires or prolongs inpatient hospitalization. Admission from the SSU itself does not count as an SAE, but an expected outcome. However, if in the investigators judgment, admission from the SSU was due to some other complication of the study protocol, rather than an expected outcome, it should be reported as an SAE

SPECIFIC REPORTABLE SAE for SSU/OU arm patients:

- Cardiac arrest

- Need for intubation or positive pressure ventilation
- It results in persistent or significant disability/incapacity (i.e., the AE results in substantial disruption of the subject's ability to conduct normal life functions).
- It is considered a significant medical event by the investigator based on medical judgment (e.g., may jeopardize the subject or may require medical/surgical intervention to prevent one of the outcomes listed above).

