10.4.4 SAFETY ANALYSES

As all cause mortality and re-hospitalizations will already be reported as part of the efficacy exploratory analyses, these will also be highlighted as safety analyses. We will also report the proportion of patients who are admitted from the SSU as well as AE/SAE's.

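### SAE capture differs by arm: ventilation is a named SAE only for SSU patients, and only admission from the SSU must pass a protocol-link test

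*Combined protocol and SAP*

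**What the plan says.** Section 8.1.2 opens with general SAE criteria that name no arm: death, a life-threatening event (one that "places the subject at immediate risk of death"), and an AE for which "It requires or prolongs inpatient hospitalization". The last carries an exception: "Admission from the SSU itself does not count as an SAE, but an expected outcome". The exception is lifted only if the investigator judges that "admission from the SSU was due to some other complication of the study protocol, rather than an expected outcome".

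Next comes the heading "SPECIFIC REPORTABLE SAE for SSU/OU arm patients", followed by cardiac arrest and "Need for intubation or positive pressure ventilation". The bullets on disability and on other significant medical events come after this heading.

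Section 8.1.1 directs AE collection, in both arms, to events beyond what is usual in an acute heart failure episode. It illustrates a reportable worsening with: "For example, a patient upgraded to ICU status from the observation or SSU". Section 8.2.3 lists mechanical ventilation, invasive or not, among events exempt from regulatory reporting, and no arm is stated. Section 8.4.1 has non-exempt AEs investigated from discharge summaries.

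Section 10.4.4 states: "We will also report the proportion of patients who are admitted from the SSU as well as AE/SAE's". Section 8.1 makes death, re-hospitalization and ED visits to 30 and 90 days safety outcomes.

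**The concern.** In an unblinded trial, an SAE count by arm is informative only if the same event counts in both arms. Here two rules depend on the arm, and they pull in opposite directions. The named list favours counting ventilation in SSU patients. The admission exception favours not counting some SSU events that lead to inpatient care.

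Little downstream corrects this. Section 10.4.5 says there is no clinical events or adjudication committee. The vote among site investigators in section 8.2.2 is optional and arises only when the local investigator cannot decide. SAEs go to the DSMB (section 8.4.2), which has no formal stopping rules and may recommend halting only for safety (section 10.4.7). Part of a difference seen there, or in the final report, could come from the definition, and part of a true difference could be masked by it.

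**Working it through.** **The rules side by side**

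| Event | SSU arm | Usual care |
|---|---|---|
| Cardiac arrest | Named SAE | No list, but normally fatal or life threatening, so an SAE |
| Intubation | Named SAE | No list; usually life threatening, so mostly an SAE |
| Non-invasive positive pressure ventilation | Named SAE | No list; depends on judging it life threatening, stay-prolonging or significant, against an AE focus (8.1.1) and an exemption (8.2.3) that discourage capture |
| Index admission, or longer stay, for expected heart failure care | Not an SAE | Normally not an SAE, because of the AE focus in 8.1.1 |
| Index admission, or longer stay, for another AE | SAE only if judged a protocol complication, or if another criterion is met | SAE with no protocol link |
| Later re-hospitalization due to an AE | No protocol link needed | No protocol link needed |

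The arms differ materially in the third and fifth rows. In the SSU arm the third row also contradicts section 8.2.3: the same event is both specifically reportable and exempt.

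**Arm size.** Section 10.5 gives SD 3.9, difference 1 day, 80% power and two-sided 0.05. Then n = 2 × (1.960 + 0.842)² × 3.9² / 1² = 238.8, or 239 per arm, consistent with the stated 240 after the O'Brien-Fleming allowance. With 10% attrition, 480 / 0.9 = 533.3, or 534 in total and 267 per arm, as stated.

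**Illustration.** The documents give no event rates and no capture shares. Everything below other than 267 is an assumption, with true risk equal in the two arms and the two kinds of event treated as separate.

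- *Ventilation.* SSU count = 267 × r; usual-care count = 267 × r × c, where c is the share caught by the general criteria. With c = 50%:
  - r = 2%: 5.3 against 2.7, difference +2.7 for the SSU arm.
  - r = 5%: 13.4 against 6.7, difference +6.7.
  - r = 10%: 26.7 against 13.4, difference +13.4.
  - With c = 100% the difference is 0.
- *Another AE requiring or prolonging inpatient care.* Usual-care count = 267 × q; SSU count = 267 × q × s, where s is the share still counted. With s = 50%:
  - q = 5%: 6.7 against 13.4, difference −6.7 for the SSU arm.
  - q = 10%: 13.4 against 26.7, difference −13.4.
  - q = 20%: 26.7 against 53.4, difference −26.7.
  - With s = 100% the difference is 0.

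**Net effect, with both shares at 50%.** For r = 10% and q = 5%: 13.4 − 6.7 = +6.7. For r = 5% and q = 5%: 6.7 − 6.7 = 0. For r = 2% and q = 10%: 2.7 − 13.4 = −10.7. Equal true risk can therefore appear as an excess, no difference or a deficit in the SSU arm.

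**The case against.** The general criteria in section 8.1.2 do most of the work. Those for death and life-threatening events have no arm limit, so a reader who infers that usual-care arrests go uncounted would be wrong, and most intubations would be caught too. A usual-care count of zero for the named events is not a credible lower bound. This stands, and it narrows the gap to ventilation, mainly non-invasive. Patients needing ventilatory support at ED disposition are also excluded (section 5.2) and AE reporting runs 5 days (section 8.4.1), so the higher assumed rates may be generous.

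A reader might also take the planned 40% admission rate (section 10.5), 267 × 0.40 = 106.8 or about 107 SSU patients, as the number of SAEs lost. It is not. It counts patients exposed to the exception, many of whom will simply need more heart failure treatment. Only those admitted for some other event unrelated to the protocol are affected, and the documents do not say how many that is. Nor does every SSU event leading to inpatient care need a protocol link: fatal or life-threatening events and later re-hospitalizations do not.

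The ICU upgrade in section 8.1.1 is only an example and does not exclude upgrades from a ward. The SSU heading may be meant as closer surveillance of a new strategy. That would justify faster reporting in one arm, but it sits inside the definition and no common definition is restored elsewhere. The generic bullets after it suggest a list that was interrupted; read literally, they too would be SSU-only.

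Finally, section 10.4.4 plans to report SAEs, not to test them, and the DSMB charter is a separate document not available here.

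**Conclusion.** The concern holds in a limited form. Total SAE counts by arm are not fully comparable, because ventilation is captured more readily in the SSU arm and some events leading to index admission are captured less readily there. The sign of the net bias cannot be known in advance. The size is not given by the documents. Under the assumed rates, and with half of the affected events counted in the disadvantaged arm, each rule moves the count by about 3 to 27 events, in opposite directions.

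The stronger inference, that safety cannot be compared between arms at all, is not supported. Death, re-hospitalization and ED visits are collected alike to 90 days, and admissions from the SSU are reported separately. Those outcomes do not, however, describe non-fatal deterioration during the index stay, which is where the definitions diverge. The conclusion rests on the text as written and on no common definition being supplied by the DSMB charter.

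**What to change.** Use one SAE definition for all randomized patients.

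1. In section 8.1.2, retitle the named list so that cardiac arrest and need for intubation or positive pressure ventilation apply in both arms, wherever they occur.
2. Move the disability and significant-medical-event bullets above that list, so that they are plainly general criteria.
3. In section 8.1.1, word the ICU-upgrade example for either the SSU or an inpatient ward.
4. Use one hospitalization criterion with no relatedness test: an expected SSU admission, or a longer ward stay, for heart failure alone is not an SAE; any other AE that leads to admission or prolongs the stay is an SAE in either arm. Relatedness is recorded separately under section 8.2.2.
5. Reconcile sections 8.1.1, 8.1.2 and 8.2.3 on ventilation. Extending the list without this step would carry the existing contradiction into both arms.
6. Keep admissions from the SSU as a separate count in section 10.4.4.

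The cost is protocol and CRF wording, site retraining, and a few more SAE forms in both arms: ventilation in usual care, and non-protocol events leading to admission in the SSU arm. Deciding whether an event is heart failure alone still rests with an unblinded investigator, so the change reduces the asymmetry without removing all judgement. Treatment, eligibility and sample size are unchanged.
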